5.5.1 Independent Data Safety Monitoring Board (DSMB)

The DSMB will be composed of 2 third party researchers and a statistician/analyst (Drs. [name] and [name] – University of Calgary, AB; [name], University of Manitoba). Safety data will be reviewed at least yearly at planned DSMB Data Review Meetings. Serious adverse events (see below) will be reported and reviewed immediately by the DSMB Chair. The DSMB will provide recommendations for continuation or early termination of the trial

based on assessment of safety. The DSMB may also make recommendations related to the selection, recruitment or retention of participants, their management and adherence to protocol-specific regimens, and the procedures for data management and quality control.

5.5.2 Ascertainment and Documentation of Adverse Events for DSMB:

- 1. At each study assessment visit, study participants will be asked by the independent outcome assessor at clinic if they have experienced any of the adverse (AE) or serious adverse events (SAE) on the list below.
- 2. In addition, the research coordinator will identify any AEs or SAEs through review of participants' hemodialysis charts at each assessment time point.
- 3. Study kinesiologist and research coordinator will also track events if noted during their interaction with patients.
- 4. Study staff will communicate with dialysis staff to inform them regarding the types of issues that constitute AEs and SAEs. Dialysis staff will be asked to report any such occurrences to study staff as soon as possible.

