7.4 Study Groups

7.4.1 Control Arm, Standard-of-care

As recommended in clinical practice guidelines for individuals with CKD, participants will receive standardized exercise counseling at baseline.^{76, 77} Although not prohibited from participating in exercise outside of the study protocol, participants in the control group will not undergo a formal structured exercise intervention and will be asked to refrain from intradialytic cycling during the 12-week intervention period. Exercise activity will be tracked via weekly self-reported log sheets. The study kinesiologist (to control for personal trainer effect) will collect log sheets weekly during the study period. Outcome measurements will occur according to the Schedule of Events (Section 7.5).

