During the initial 3 intradialytic exercise sessions, the study kinesiologist will supervise participants closely. Following 3 sessions (or more if required), HD unit staff will assist with set up of the cycle ergometers and monitoring during exercise sessions.

During the *intensive phase* of the intervention, the study kinesiologist will check in on a weekly basis (at a minimum) with participants and staff to address problems and questions as needed. Subsequently, during the *maintenance phase* of the intervention, the kinesiologist will check in every two weeks to help with intensity adjustment, encouragement, motivation and troubleshooting. All exercise activity performed outside of HD, including resistance training will be tracked weekly by self-report using home log sheets during the intervention phase and then bimonthly until study end (see Section 7.4.5 Study Intervention Design Schematic).

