8.1 Specification of Safety Parameters

All adverse events (AEs) and serious adverse events (SAEs) will be classified by body system and preferred term according to the Medical Dictionary for Regulatory Activities (MedDRA). AEs and SAEs will be summarized as the frequency of each event in the treatment group.

Frequency tables by treatment group and category of event (e.g., serious, related to study therapy, causing the discontinuation of study intervention) and by National Cancer Institute – Common Terminology Criteria for Adverse Events (NCI-CTCAE) severity grade will be presented. Selected laboratory values will also be summarized in the treatment group using the mean and standard deviation of the change from baseline at scheduled visits.

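### Adverse events noted in passing during staff contacts are captured unequally by design and pooled by arm without their source, so soft-event frequencies could be inflated in the exercise arm

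*Combined protocol and SAP*

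**What the plan says.** Section 5.5.2 lists four ascertainment routes, numbered here as there.

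1. Structured questioning: "At each study assessment visit, study participants will be asked by the independent outcome assessor at clinic" about a fixed list of events.
2. Chart review: "the research coordinator will identify any AEs or SAEs through review of participants' hemodialysis charts at each assessment time point".
3. Events noticed in passing: "Study kinesiologist and research coordinator will also track events if noted during their interaction with patients".
4. Unit staff reports, after staff have been told what counts as an event: "Dialysis staff will be asked to report any such occurrences to study staff as soon as possible".

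For controls, section 7.4.1 says the study kinesiologist "will collect log sheets weekly during the study period" and gives control of a trainer effect as the reason. Section 7.1 sets one log schedule for both groups: weekly for 12 weeks, then every 2 weeks for 40 weeks.

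For the exercise arm, section 7.4.2 plans at least weekly kinesiologist check-ins in the intensive phase and two-weekly ones in the maintenance phase. It adds 8 education sessions (the first 4 lasting an hour each) and 4 weekly one-on-one resistance-teaching sessions. It also says: "During the initial 3 intradialytic exercise sessions, the study kinesiologist will supervise participants closely". After that, "HD unit staff will assist with set up of the cycle ergometers and monitoring during exercise sessions".

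Section 8.1 plans "Frequency tables by treatment group and category of event", and by severity grade. Neither 8.1 nor section 9 mentions the route by which an event was found.

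**The concern.** The yield of route 3 depends on how often, how long and in what setting staff are with a participant, and these differ by arm. Route 4 is worded alike for both arms, but unit staff watch cycling in one arm only.

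Several listed non-serious events in section 5.5.3 are soft: muscle aches, cramping, increasing fatigue. Such events tend to be recorded when someone is present to hear of them. If more of them are heard in one arm, that arm's frequency rises with no difference in true risk. Without a source field, nobody reading the table can tell the two explanations apart, and a source not recorded when the event is found may not be recoverable later.

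The table will be read as evidence. Section 2.3.1 notes that earlier intradialytic exercise studies were not powered for safety, and section 8.5 has the DSMB look at safety data for each arm.

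**Working it through.** The plan gives no adverse event rate, detection probability or adverse event test, so there is no stated figure to reproduce. Two checks are possible.

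**Check 1: kinesiologist contacts by arm**

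Inputs are from sections 7.1, 7.4.1 and 7.4.2. I assume that the exercise arm's log collection and check-in are one contact and that the two-weekly phase starts at week 13.

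- Control, weeks 1-12: 12 log collections.
- Exercise, weeks 1-12, lowest: 12, if all teaching and supervision fall on the weekly check-in. Ratio 12/12 = 1.0.
- Exercise, weeks 1-12, only the education sessions separate: 12 + 8 = 20. Ratio 20/12 = 1.67.
- Exercise, weeks 1-12, every session separate: 12 + 8 + 4 + 3 = 27. Ratio 27/12 = 2.25.
- Weeks 13-52: 40/2 = 20 in each arm.
- Whole year: control 12 + 20 = 32; exercise 32 to 27 + 20 = 47. Ratio 1.0 to 47/32 = 1.47.

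The weekly check-ins and the 3 supervised sessions are stated as minimums, so 27 is not a strict ceiling. Contact time differs more than the count does: collecting a log sheet is set against hour-long teaching and supervised cycling.

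**Check 2: what unequal noting could do to the table (all inputs assumed)**

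Let the true risk p be equal in both arms. Let the common routes find a share c of affected participants, and let staff contacts find a share a of the remainder. The detected share is d = c + (1 - c) × a, and the apparent risk ratio is d(exercise)/d(control), whatever the value of p. Take a = 0.1 in control and 0.2 or 0.4 in exercise.

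| c | d control | d exercise (a = 0.2; 0.4) | Apparent risk ratio |
|---|---|---|---|
| 0.5 | 0.55 | 0.60; 0.70 | 1.09; 1.27 |
| 0.7 | 0.73 | 0.76; 0.82 | 1.04; 1.12 |
| 0.9 | 0.91 | 0.92; 0.94 | 1.01; 1.03 |

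With 75 per arm and p from 0.2 to 0.6, the chance that a two-sided 0.05 test would show a nominal excess in the exercise arm is about 3% to 21%, against 2.5% with equal detection. The top value is p = 0.6, c = 0.5, a = 0.4, with detected risks 0.33 and 0.42. The plan has no such test; the figure only shows how often an apparent excess of that size could arise.

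**How much the common routes might recover**

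After baseline, section 7.2 puts visits at 12, 26 and 52 weeks, so recall at questioning covers 12, 14 and 26 weeks. The trial's own symptom questionnaire (Appendix 3.1) asks about one week. An ache or a bout of fatigue that was never charted may be lost over such intervals. An admission or a fracture is unlikely to be.

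**The case against.** The strongest reply is that the design already limits the problem. Controls see the same kinesiologist weekly, for a stated reason, and the schedules match after week 12. Every participant is asked about the same list by an independent assessor, and every chart is reviewed, so route 3 adds only what the other routes miss. Section 8.2.3 restricts reporting to grade 2 or higher, which removes the mildest complaints. The by-arm presentation is descriptive: no test is planned, and safety is not among the trial's stated outcomes. All of this stands. It limits the possible bias but does not remove it, and nothing in the plan lets a reader check its size.

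A reader might infer a fourfold surveillance gap by adding 36 monitored cycling sessions to 12 check-ins and setting 48 against 12. The documents do not support that. After the first sessions the monitoring is by unit staff, which is route 4. Controls also attend in-centre dialysis under the same staff; on the same three-weekly schedule the count would be 48 against 48. What differs is how closely unit staff watch during cycling, not the number of dialysis sessions.

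A further objection concerns the remedy. Removing routes 3 and 4 from the by-arm tables altogether could hide harm, because chest pain or arrhythmia while exercising is on the serious list and may be seen only by staff present at cycling. That objection is sound, and the fix below keeps those events in.

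**Conclusion.** Unequal capture through route 3 is built into the plan, and the source of each event is not recorded. The kinesiologist contact ratio is 1.0 to 2.25 in weeks 1-12 and 1.0 to 1.47 over 52 weeks, depending on how many teaching and supervised sessions are separate contacts. By-arm frequencies of soft events could be inflated in the exercise arm. Under the assumed detection values the apparent risk ratio runs from 1.01 to 1.27, and it is near nil (1.01 to 1.03) if the common routes find 90% of affected participants. The documents fix none of those values.

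It would be tempting to conclude that exercise will look more harmful through surveillance alone. The documents support only that it could, for soft non-serious events. Deaths, admissions and fractures are unlikely to depend on this route. The point is a cheap improvement to how the safety data are recorded and shown; it does not undermine the primary comparison.

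**What to change.** 1. Add a source field to the adverse event form with codes for routes 1 to 4, allowing more than one, so that an event first noted in a contact and later reported to the assessor carries both codes.
2. Keep the all-events by-arm table of section 8.1 and all reporting to the DSMB unchanged.
3. Add a by-arm table of non-serious events found by route 1 or 2, labelled as the like-for-like comparison, and show events found only by routes 3 or 4 separately by source.
4. Keep every serious adverse event in the by-arm tables, whatever its source.
5. Optionally, ask the same scripted adverse event question at the log collection already scheduled in both arms, with its own source code.

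The cost is one form field, one table and a few sentences in sections 5.5.2 and 8.1, plus a short script if item 5 is taken up. The like-for-like table will omit some events found only in contacts; these remain in the all-events table. It also equalises the schedule of ascertainment rather than everything behind it, since closer watching may still lead to more charting.

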5.5.3 List of Adverse Events to Be Collected for DSMB

Adverse Events:

- 1. Fistula blow
- 2. Muscle aches or pains
- 3. Symptomatic Intradialytic hypotension (BP < 90 mmHg or 20 mmHg drop from baseline associated with symptoms such as headache, cramping, dizziness, nausea)
- 4. Intradialytic cramping
- 5. Increasing fatigue
- 6. Symptomatic hypoglycemia (sugar < 4 associated with typical symptoms of hypoglycemia)
- 7. Fall
- 8. Foot ulcer

Serious Adverse Events:

- 1. Chest pain while exercising (either intradialytic or outside of dialysis)
- 2. Arrhythmia while exercising (either intradialytic or outside of dialysis)
- 3. Unstable hemodialysis necessitating transfer to emergency post hemodialysis
- 4. Tendon rupture
- 5. Fall with fracture
- 6. Admission to hospital for any cause
- 7. Acute coronary syndrome
- 8. Death from any cause

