8.1.2 Definition of Serious Adverse Events (SAEs)

An SAE or reaction is any untoward medical occurrence that at any dose leads to any of the following events:

- 1. Death. A death that occurs during the study or that comes to the attention of the investigator during the protocol-defined follow-up must be reported whether it is considered to be treatment related or not.
- 2. A life-threatening event. A life-threatening event is any adverse therapy experience that, in the view of the investigator, places the patient or subject at immediate risk of death from the reaction as it occurred.
- 3. Inpatient hospitalization or prolongation of existing hospitalization.
- 4. Persistent or significant disability.
- 5. An event that requires intervention to prevent permanent impairment or damage. An important medical event that may not result in death, be life threatening, or require hospitalization may be considered an SAE when, based on appropriate medical judgment, it may jeopardize the subject and may require medical or surgical intervention to prevent one of the outcomes listed above.
- 6. Congenital anomaly or birth defect.

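### Sections 5.5.3 and 8.1.2 define a serious adverse event differently and are not reconciled, so the by-arm SAE count and the reporting route depend on the section used

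*Combined protocol and SAP*

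**What the plan says.** Section 5.5.3 has a second list, titled as serious adverse events, of eight items to be collected for the DSMB. The first is "Chest pain while exercising (either intradialytic or outside of dialysis", the second "Arrhythmia while exercising (either intradialytic or outside of dialysis" and the third "Unstable hemodialysis necessitating transfer to emergency post hemodialysis". Tendon rupture, fall with fracture, hospital admission, acute coronary syndrome and death complete it. No item carries a severity grade, and only admission and death are themselves outcomes in the sense of section 8.1.2.

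Section 8.1.2 takes the other approach: "An SAE or reaction is any untoward medical occurrence that at any dose leads to any of the following events". It then names death, immediate risk of death, hospitalization or its prolongation, lasting disability, need for intervention to prevent permanent damage, and congenital anomaly. Its fifth item adds that an important medical event outside these outcomes "may be considered an SAE when, based on appropriate medical judgment, it may jeopardize the subject".

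Section 8.1 specifies the safety output: "Frequency tables by treatment group and category of event (e.g., serious, related to study therapy, causing the discontinuation of study intervention", and so on. It does not say which definition decides that an event is serious.

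On exposure, section 7.4.1 says controls "will be asked to refrain from intradialytic cycling during the 12-week intervention period". It also leaves them free to exercise outside the study.

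**The concern.** When two sections of one protocol use the same term for different sets of events, two careful people can produce different SAE counts from the same case report forms. Staff reporting events face the same problem, because each definition is attached to its own procedure.

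The difference is also not neutral between arms. Two of the items found only in 5.5.3 depend on the participant exercising at the time, and exercise is what the trial randomizes. Section 2.3.1 says that earlier intradialytic exercise studies were not powered for safety, so the by-arm SAE table of this trial is likely to be read closely. An imbalance in it should reflect serious outcomes, not the choice of section.

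**Working it through.** The plan gives no SAE rate, expected SAE count or safety power, so there is no figure to reproduce. The check is a comparison of passages plus a count of scheduled exposure.

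**1. The 5.5.3 items against 8.1.2.**

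| 5.5.3 item | Meets 8.1.2 automatically? |
|---|---|
| Chest pain while exercising | No; only through an outcome or by judgment |
| Arrhythmia while exercising | No; as above |
| Unstable dialysis with emergency transfer | No; admission is not required |
| Tendon rupture | No; disability, intervention or judgment may apply |
| Fall with fracture | No; as above |
| Acute coronary syndrome | No outcome stated, but likely through admission or risk of death |
| Admission for any cause | Yes |
| Death | Yes |

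Five of the eight items can clearly occur without meeting 8.1.2. Brief chest pain on the bike that settles by itself is the plainest case.

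**2. The 8.1.2 criteria against 5.5.3.** A life-threatening event without admission, lasting disability, and intervention to prevent permanent damage have no item of their own on the list. The mismatch runs both ways.

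**3. Which procedures use which definition.**
- Section 5.5.1: "Serious adverse events (see below) will be reported and reviewed immediately by the DSMB Chair". The cross-reference points to the 5.5.3 list.
- Section 5.5.2: the visit question to participants is about the listed events.
- Section 8.4.2: the SAE report, due within 7 working days, is for events meeting the criteria and definition of an SAE, which within section 8 is 8.1.2.
- Section 8.1: a serious category by arm, with no definition named.

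Both definitions are therefore in operation, and neither section refers to the other.

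**4. Opportunity for the two exercise-linked items.** Inputs: cycling 3 times a week and resistance exercise 2 times a week, each for 12 weeks (section 7.4.6), and 75 participants per arm (section 9.2).
- Cycling: 3 × 12 = 36 sessions per participant.
- Resistance: 2 × 12 = 24 sessions per participant.
- Total: 36 + 24 = 60 per participant, and 60 × 75 = 4,500 for the intervention arm, plus one maximal cycle test each.
- Control arm: 0 scheduled training sessions.

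The shuttle walk is done in both arms at four visits, three of them after randomization. Controls may exercise on their own (section 7.4.1), and after the intervention phase either arm may cycle where the unit offers it (section 7.4.3). Control exposure is therefore lower by design but not zero.

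The 12-week figure is itself inconsistent. Section 7.4.2 (resistance), section 7.6 and Appendix 2 speak of 26 weeks, and these passages need reconciling. With 26 weeks for both components the count would be (3 + 2) × 26 = 130 sessions per participant, or 130 × 75 = 9,750, still against none scheduled for controls. The direction does not change.

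**5. The same symptom at rest.** Chest pain or arrhythmia at rest appears in neither 5.5.3 list. It reaches the serious list only through admission, emergency transfer, acute coronary syndrome or death. Under 5.5.3 the same episode is serious on a bike and unlisted in a chair.

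**The case against.** The strongest reply is that section 8 is self-contained. Section 8.1 specifies the tables, 8.1.2 is its own subsection, and 5.5.3 is headed as a collection list for the DSMB. On that reading the tables already use 8.1.2 and only a cross-reference is missing. This may well be the intended reading. It stands against any claim that the table does count the listed events, which the documents do not establish. It does not remove the defect: 5.5.3 uses the same name, 5.5.1 and 5.5.2 act on it, and 8.1 is silent.

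A reader might infer that only the intervention arm can have the two exercise-linked events. The documents contradict this: controls may exercise, walk the shuttle test and may cycle later, and both items cover exercise away from dialysis.

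A reader might also infer that serious events off the list are lost to the DSMB. That is not supported. Section 8.5 gives the DSMB listings of all SAEs, section 8.4.1 has it review all data, and sections 5.5.2 and 8.3 add chart review, staff reports and unsolicited complaints as sources.

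Two further replies stand in part. The judgment clause in 8.1.2 brings some listed events in, so the definitions overlap more than the bare outcome list suggests. And an event that happens because a participant was assigned to exercise is a genuine harm of assignment, so counting it by arm is not bias in itself. The distortion arises because the same event at rest is not listed. Tables by preferred term, relatedness and grade would also leave such events visible, and no formal between-arm SAE test is planned.

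**Conclusion.** The concern holds in limited form. The two definitions differ in both directions, both are in use, and nothing says which governs the by-arm tables. If the list were used, the SAE comparison would be tilted by unequal opportunity, because exercise exposure is much larger, though not exclusive, in the intervention arm.

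It is tempting to multiply scheduled sessions by a plausible event rate and quote an excess of SAEs. The documents do not support that: they give no rate, the session counts assume full attendance against an anticipated 30% dropout (section 9.2), and control exposure is unknown. No numerical size is claimed. The conclusion rests on the wording of the sections and on the direction of the scheduled exposure. It concerns safety reporting and leaves the primary efficacy analysis untouched.

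**What to change.** Reconcile the sections as follows.

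1. State in 8.1 that 8.1.2 decides what is serious in the by-arm SAE tables, for both arms.
2. Relabel the second list in 5.5.3 as events of special interest. State that each item stays in every DSMB, research ethics board (REB) and SAE-report route it has now, so that the relabelling removes nothing from review.
3. Add to the case report form a yes/no flag for whether each listed event meets 8.1.2.
4. Record chest pain and arrhythmia in both arms whether or not they occur during exercise, noting which.
5. Tabulate the listed events separately by arm, and show the exercise-linked ones also per exercise session. The self-reported logs kept in both arms (section 7.7) can supply the denominator, with the limits of self-report.

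The cost is one form field, one extra table and slightly wider event recording. Appendix 5 shows that participants were already on study in March 2020, so events recorded before the change would need flagging from source documents, preferably by someone unaware of the arm. Earlier resting episodes may be only partly recoverable from charts.
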